### **9.7.6 Sensitivity analysis**

At least the following sensitivity analyses will be performed:

1. All analyses will be performed using an alternate outcome definition using the primary hospitalization discharge diagnosis only (ICD-9-CM 577.0 or ICD-10-CM K85 acute pancreatitis).
2. Exclude cases with ICD-10 K85.2x (Biliary acute pancreatitis) and K85.3x (Alcohol induced acute pancreatitis) and also report the percentage of these cases in overall identified acute pancreatitis cases.
3. Implement an intention-to-treat approach, where all users maintain assignment to their original treatment arm throughout a fixed follow-up period 12 months after first exposure. Users of empagliflozin or a comparator oral non-incretin/non-SGLT2i-containing glucose lowering drugs will be considered exposed from the date of first prescription claim (following a 6-month period without a prescription claim for their index medication) until earliest claim for acute pancreatitis or until one of the following censoring criteria have been met: death, end of registration, or study end. In this analysis, patients discontinuing therapy will not be censored.
4. Subgroup analyses will be performed focusing on patients with and without history of eCVD in the 12 months prior to the index date
5. It is known that Diabetic ketoacidosis (DKA) can be complicated with pancreatitis. As a sensitivity analyses, cases with prior DKA will be excluded.
6. In dual or triple therapy cohorts when the non-index medication (metformin) is discontinued or switched patients will be censored.
7. Considering grace period of 90 days for all medications.

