### **9.3.2      Outcomes**

#### **9.3.2.1      Primary outcomes**

In this study we will use a modified version of an algorithm developed and validated in the [REDACTED] with a sensitivity of 89.8% and a specificity of 79.4% [[R20-3555](#), [R20-3554](#)]. In the original algorithm, only the Logical Observation Identifiers Names and Codes (LOINC) were used for the lipase measurement but since these codes are only available for a subset of patients in Marketscan and Optum databases, to accommodate database needs, the equivalent Current Procedural Terminology (CPT) codes were added to the algorithm. This modified algorithm is:

- The presence of an acute pancreatitis diagnosis from any of the inpatient (not restricted to the primary diagnosis), outpatient, or emergency contacts diagnoses (ICD-9-CM 577.0 or ICD-10-CM K85)  
AND
- A lipase measure within +/- 7 days of the acute pancreatitis diagnosis (using LOINC code of 3040-3 and 2572-6 or CPT code of 83690 for lipase)  
AND
- An abdominal ultrasound (using CPT codes of 76700 and 76705) within +/- 7 days of the acute pancreatitis diagnosis

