### **9.7.1 Definitions**

- Index date: Date of the first recorded claim for a qualifying prescription of an index medication as a new user.

- Follow-up: Starts from the day after the index date until the first qualifying event has been met (see [Table 2](#) and [3](#)).
- Look-back period: Patients are required to have at least 6 months of continuous registration in the database prior to initiation of an index medication. The look-back period is defined as 6 months prior to the index date and including the index date. The look-back period was specified to confirm new medication use (i.e. having a first prescription claim for empagliflozin or other oral non- incretin/non-SGLT2i-containing hypoglycaemic without use of these medications in the prior 6 months) and describe baseline parameters, such as prior medical history and medications.
- Grace period: 30 days in main analysis [[c18659315-02](#)] and 90 days [[R18-1760](#), [RRA-21430](#), [P20-07536](#)] in sensitivity analysis.

Table 2 Definitions for study end date

Reason for End of Study or censoring (earliest date of options below)	Definition for End Date
Acute pancreatitis event	Date of the first acute pancreatitis using ICD9 or ICD10 codes
Switch of index medication to another hypoglycaemic agent; see Table 3	Last date of known prescription coverage (date of last prescription fill plus days' supply minus one day) and a grace period equal to 30 days. Exposure time will not extend past the date of the first prescription claim for the newly prescribed agent*
Addition of incretin-based therapy (with continuation of index therapy)	Date of the prescription claim for the added incretin therapy
Addition of SGLT2i (with continuation of index therapy)	Date of the prescription claim for the added SGLT2i therapy
Addition of insulin (with continuation of index therapy)	Date of the prescription claim for the added insulin therapy
Addition of the within treatment line comparator index drug; see Table 3 (with continuation of index therapy)	Date of the prescription claim for the added treatment line comparator index drug
Discontinuation of index drug	Last date of known prescription coverage (date of last prescription fill plus days' supply minus one day) and a grace period equal to 30 days*
End of study data	Date of death#, Date of end of registration, Date of Study End

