### **9.9.3 Misclassification**

To minimize misclassification of the recorded patient characteristics, previously validated algorithms or code-lists will be used whenever available. Code-lists were reviewed by qualified medical reviewers prior to implementation. A preliminary study to optimize and validate the algorithm for identification of cases of acute pancreatitis using ICD-9-CM and ICD-10-CM codes was conducted in the [REDACTED]

Some of the major risk factors for acute pancreatitis (e.g. alcohol use, obesity, biliary pathology not requiring reimbursement) are under-reported in claims databases. A similar limitation exists for use of medications known to cause acute or chronic pancreatitis, and it is impractical to account for all of these, even if the data are available. Conversely, the incidence of acute pancreatitis can be overestimated because providers may have used the acute pancreatitis code, abdominal ultrasound or serum lipase measurement to rule out the diagnosis of acute pancreatitis. To mitigate this risk, diagnosis for acute pancreatitis will be assessed using an algorithm that has been validated in the [REDACTED] and shown to have a sensitivity of 89.8% and a specificity of 79.4% [R20-3554]. However, this algorithm does not allow for etiological or pathophysiological description of the type of acute pancreatitis.

Further, the study utilizes a modified as-treated approach as the primary analysis, which could result in exclusion of some cases of acute pancreatitis due to censoring criteria (i.e., patients would be classified as not experiencing acute pancreatitis, but the event could have occurred after censoring). In order to address this, we will perform a sensitivity analysis using an ITT approach. This approach is more conservative and maintains drug classification similar to randomization; however, there is greater risk of exposure misclassification. Ultimately, however, this method will allow for evaluation of potentially additional cases of acute pancreatitis that transpire during the study period given the more limited censoring criteria.

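### Sensitivity analysis 2 can remove only ICD-10-coded cases, so ICD-9 cases stay in the HR whatever their cause and lower the percentage if it is read as an aetiology share

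*Protocol*

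**What the plan says.** Protocol 9.3.2.1 identifies a case by a diagnosis under "ICD-9-CM 577.0 or ICD-10-CM K85" together with a lipase test and an abdominal ultrasound. Table 2 in 9.7.1 dates the event as "Date of the first acute pancreatitis using ICD9 or ICD10 codes". Item 1 of 9.7.6 uses the same pair of codes for its alternative outcome.

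The code lists (protocol Annex 3, SAP Annex 1) give one ICD-9 code for acute pancreatitis, 577.0, and K85.xx for ICD-10. Annex 3 cites a 2015 ICD-9-CM table, and patients can enter from 1 August 2014.

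Item 2 of 9.7.6 works on ICD-10 sub-codes alone: "Exclude cases with ICD-10 K85.2x (Biliary acute pancreatitis) and K85.3x (Alcohol induced acute pancreatitis"). It then asks the analyst to "also report the percentage of these cases in overall identified acute pancreatitis cases". It gives no rule for ICD-9 cases.

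SAP 10.6 only refers back to the protocol. Protocol 9.7.7 and SAP 9.2 treat a condition without a code as not present.

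**The concern.** Item 2 asks whether the result survives once two named causes are taken out. A case recorded only as 577.0 cannot satisfy a K85.2x or K85.3x rule, so it is kept even if it was biliary or alcohol-induced. The missing-code convention would count it as neither, although its cause is unknown.

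This has two consequences. The sensitivity HR still contains some of the cases it was meant to drop, so part of any agreement with the main HR would be built in. And the percentage, which the labels in item 2 invite a reader to take as an aetiology share, is lowered by cases that could never enter its numerator.

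**Working it through.** **Scale.** The planned size gives the expected number of cases. Inputs from protocol 9.5 are π1 = π2 = 0.0022, null ratio 1.5, one-sided α = 0.05, power 80%, 1:1 allocation and one year of follow-up. The Farrington-Manning formula is

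n per group = [z(0.95)·√V0 + z(0.80)·√V1]² / (π2 − 1.5·π1)²

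- V0 uses the rates fitted under the null (0.001760 and 0.002640) and equals 0.006585.
- V1 = 0.0022 × 0.9978 × (1 + 1.5²) = 0.007134.
- n = 34,585.41, which matches the protocol's 34585.4.

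Expected cases in both groups: 2 × 34,585.4 × 0.0022 = 152.2.

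**Percentage.** Let t be the true share of biliary and alcohol cases and s the share of all cases coded in ICD-9. The documents give neither, so both are assumptions. I also assume that t is the same in both coding eras, that ICD-10 sub-coding of cause is complete, and that the two sub-codes carry the labels item 2 gives them.

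- Reported percentage = t(1 − s), a relative shortfall of s.
- Target cases wrongly kept = s·t × 152.2.
- Their share of the cases kept = st / (st + 1 − t).

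| t | s | Reported | ICD-9 cases | Target cases kept | Share of kept cases |
|---|---|---|---|---|---|
| 50% | 0% | 50% | 0 | 0 | 0% |
| 50% | 5% | 47.5% | 7.6 | 3.8 | 4.8% |
| 50% | 10% | 45% | 15.2 | 7.6 | 9.1% |
| 50% | 20% | 40% | 30.4 | 15.2 | 16.7% |
| 20% | 20% | 16% | 30.4 | 6.1 | 4.8% |
| 60% | 20% | 48% | 30.4 | 18.3 | 23.1% |

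**HR.** As an illustration, take a true HR of 1.5 for other causes and 1.0 for biliary and alcohol cases, t = 0.5, with t and s as comparator-arm shares.

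- Main HR: 0.5 × 1.5 + 0.5 × 1.0 = 1.25.
- Complete exclusion: 1.50.
- Item 2 as written: (1.5 × 0.5 + s × 0.5) / (0.5 + s × 0.5). This is 1.48 at s = 5% and 1.42 at s = 20%.

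The log-HR moves by 0.016 to 0.057 towards the main result. About 80 to 91 cases are kept, so its standard error is roughly 2/√80 = 0.22 to 2/√91 = 0.21. The shift is at most about a quarter of one standard error.

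**The case against.** The strongest reply is that the percentage is right as defined. Item 2 asks for the sub-coded cases as a fraction of all identified cases, and that count is correct. This stands: the figure is too low only when read as an aetiology share.

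The size cannot be established either. The documents give no changeover date between coding systems and no case count by system, and the ICD-9 share could be near zero. This also stands, and is why the figures above are scenarios.

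Matching on calendar quarter of initiation (9.7.2) should make coding era similar in the two matched arms, so the effect on the HR is dilution and not a clear between-arm bias. Gallstone disease and alcohol problems are also listed covariates (9.3.3). I accept both points, though the first does not extend to any unmatched HR.

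A reader might infer that 9.9.3 contradicts item 2, because it says "this algorithm does not allow for etiological or pathophysiological description of the type of acute pancreatitis". The documents do not support that. The sentence describes a limit of the validated algorithm (diagnosis code, lipase, ultrasound). Item 2 uses further code digits on top of it, in a sensitivity analysis. A disclosed limit and a partial check can stand together.

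Finally, cutting all follow-up to the ICD-10 period would need delayed entry for early initiators. That loses their first time on drug and weakens the new-user design. This objection is sound, and the remedy below avoids it.

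**Conclusion.** The point holds as a structural gap in one sensitivity analysis. ICD-9 cases cannot be removed from the HR and cannot enter the numerator of the percentage, and nothing elsewhere in the protocol or SAP provides for them.

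The relative shortfall in the percentage equals the ICD-9 share of cases: 47.5% to 40% in place of 50% if that share is 5% to 20%, and none if it is zero. The HR is pulled towards the main HR, by well under one standard error in the illustration.

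A reader might infer that the percentage is miscalculated or that the arms are biased against each other. The documents support neither: the sub-code count is correct as defined, and quarter matching should balance coding era in the matched cohorts. The primary analysis and the sample size are untouched. The sub-code labels cannot be verified from the documents, whose code lists show only K85.xx, and the finding does not depend on them. This is a minor, worthwhile correction.

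**What to change.** Amend item 2 of 9.7.6, with matching text in SAP 10.6:

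1. Compute the percentage over ICD-10-coded cases only. Report ICD-9 cases as unclassifiable by cause, with their number by arm and by database.
2. Keep the full-cohort HR, labelled as an incomplete exclusion.
3. Add an HR limited to matched pairs in which both index dates fall in the ICD-10 coding period. Beside it, give the main-definition HR in the same pairs, so that any change can be attributed to case definition and not to calendar period. The plan must state the date at which that period starts. Requiring both index dates matters most if matching falls back to calendar year.

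This costs a few lines of text, an index-date filter and one extra pair of models. The price is fewer events in the added version, and so a wider interval, in this one sensitivity analysis. No early time on drug is lost for the pairs retained, and the main analysis does not change.

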### 9.7.2 Propensity score approach

Decisions to begin a specific hypoglycaemic agent are influenced by demographic, medical, and clinical factors, and same factors might be associated with the outcomes of interest. The propensity score is the predicted probability of being assigned to a particular treatment conditional on a set of observed covariates. Because the models predict the probability of being treated with the exposure drug and not the probability of experiencing the outcome, a high number of variables can be used in the predicting regression model [[P12-04844](#), [R14-5241](#), [R14-5284](#), [R14-5389](#)].

Propensity scores for the comparison of empagliflozin vs. study comparator will be generated. Furthermore, given the different inclusion/exclusion criteria used for each treatment line cohort, the propensity scores will be cohort specific (i.e., propensity scores will be calculated for the monotherapy, dual therapy and triple therapy cohorts separately).

As a first step, a propensity score is estimated for each cohort member at the index date, based on the values of the observed covariates during the look-back period. In this study, propensity scores will be estimated by conducting multivariable logistic regression modelling and incorporating measured potential predictors of therapy as independent variables and exposure group status (empagliflozin group vs. comparator) as the outcome.

We will use PS matching to balance a number of covariates. Key advantages of PS matching are that large numbers of covariates can be adjusted even when studying infrequent outcomes, the achieved covariate balance can be documented, multiple outcomes can be studied after a single matching process, [R13-1120] and patients who cannot find comparable pairs will be implicitly dropped out of the analysis increasing the validity of findings [R17-1404].

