The propensity score will be used to match patients in a 1:1 ratio using a nearest-neighbor algorithm and calipers of width equal to 0.2 of the standard deviation of the logit of the estimated propensity score [R13-3590, R18-2599, R16-1227]. A 1:n variable ratio matching will not be used as it involves several complications while providing only a minimal gain in estimation precision [R17-1267]. If balance is not achieved, the PS model will be refitted using interaction terms [R18-2599]. PS balance achievement will be inspected by tabulating all patient characteristics by treatment status and by assessing the standardized differences. Any patient characteristics with a standardized difference of >10% will be considered for additional post-matching adjustment [R13-3590].

With the publication of EMPA-REG OUTCOME trial results in September 2015 and the approval of a separate indication to reduce the risk of cardiovascular death in adults with T2DM and established cardiovascular disease by the US FDA in December 2016, the characteristics of patients initiating empagliflozin has likely changed during the study period. To account for patient characteristics changing over time, patients will be matched on the calendar quarter-year of initiation of the study medication. If we lose too many patients using this method, we may instead decide to match on year of initiation of index medication and then include calendar quarter-year variable in the PS model.

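### The eCVD subgroup HRs have no propensity score, match or balance check of their own in the visible plan, so a modest false subgroup difference could arise unseen

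*Protocol*

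**What the plan says.** Protocol section 9.7.6, item 4, is one sentence: "Subgroup analyses will be performed focusing on patients with and without history of eCVD in the 12 months prior to the index date". It names no PS, match, balance table or comparison of the two HRs.

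The matching method is in section 9.7.2:

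- Level of the PS: "the propensity scores will be cohort specific (i.e., propensity scores will be calculated for the monotherapy, dual therapy and triple therapy cohorts separately".
- Match: "The propensity score will be used to match patients in a 1:1 ratio using a nearest-neighbor algorithm". The only other matching variable is time: "patients will be matched on the calendar quarter-year of initiation of the study medication", with calendar year as the fallback.
- Balance check: "PS balance achievement will be inspected by tabulating all patient characteristics by treatment status and by assessing the standardized differences". A characteristic with a "standardized difference of >10% will be considered for additional post-matching adjustment".
- Interaction terms are conditional: "If balance is not achieved, the PS model will be refitted using interaction terms".
- The same section explains a change over time in who starts empagliflozin by, among other things, the "approval of a separate indication to reduce the risk of cardiovascular death in adults with T2DM and established cardiovascular disease".

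Section 9.3.3 collects baseline covariates over 6 months, names CVD as an example, and says that some of them will enter the PS. SAP Annex 3 lists the cardiovascular conditions individually. SAP sections 10.2 and 10.6 refer back to the protocol for the PS and the sensitivity analyses.

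**The concern.** Balance in a whole matched cohort does not imply balance inside a subgroup of it. A main-effects PS can be expected to balance covariates within eCVD groups if it contains the subgroup variable and if predictors of treatment act alike in both groups. The protocol gives reason to doubt each condition. A cardiovascular indication makes it plausible that prescribing works differently in patients with eCVD. And eCVD over 12 months is not the same variable as CVD captured over 6 months.

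If the first condition fails, a pancreatitis risk factor can be over-represented among empagliflozin users with eCVD and under-represented among those without. The two imbalances can cancel in the overall table, and then the stated trigger for interaction terms does not fire.

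At stake is the reading of the one subgroup comparison in the plan. Section 7 of the protocol names eCVD as a risk factor for pancreatitis, so a false signal or false reassurance in these patients would be noticed. A reader without balance tables per subgroup could not tell it from a real effect.

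**Working it through.** **1. The plan's own figure.** Protocol section 9.5 gives a rate of 0.0022 in both groups, ratio limit R = 1.5, one-sided alpha 0.05, power 80%, 1:1 allocation and 1 year of follow-up. The Farrington-Manning formula is n = (z_alpha √V0 + z_power √V1)² / (p2 − R p1)².

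- The constrained estimate under H0 is q = 0.00176, so V0 = R² q(1−q) + Rq(1−Rq) = 0.006585.
- V1 = R² p1(1−p1) + p2(1−p2) = 0.007134.
- n = (1.645 × 0.08115 + 0.8416 × 0.08446)² / 0.0011² = 34,585 per group. The stated 34,585.4 is reproduced.
- Expected events: 34,585.4 × 0.0022 = 76 per arm, about 152 in all.

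**2. Can opposite imbalances cancel?** The documents give none of the next inputs, so they are assumptions: eCVD share 30%, a risk factor with 10% prevalence, and a risk ratio (RR) of 2 to 5 for pancreatitis.

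- With eCVD, let the prevalence be 0.13 on empagliflozin and 0.07 on SU. The standardized difference is about +0.20.
- Without eCVD, cancellation needs a difference of 0.06 × 0.30/0.70 = 0.0257 the other way: 0.0871 against 0.1129, a standardized difference of about −0.085.
- Overall the difference is 0.00, so the 10% rule passes.
- With no drug effect, HR = [1 + (RR−1) p_empa] / [1 + (RR−1) p_SU].

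| RR | HR with eCVD | HR without eCVD | Ratio |
|---|---|---|---|
| 2 | 1.13/1.07 = 1.06 | 1.087/1.113 = 0.98 | 1.08 |
| 3 | 1.26/1.14 = 1.11 | 1.174/1.226 = 0.96 | 1.15 |
| 5 | 1.52/1.28 = 1.19 | 1.348/1.452 = 0.93 | 1.28 |

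**3. Does the planned match produce this?** Simulation, one run per scenario: 120,000 patients, about 31,500 pairs, main-effects logistic PS, 1:1 nearest neighbour, caliper 0.2 SD of the logit, true HR 1 in both subgroups. The effect of the risk factor on prescribing was set to log-odds 0.3, 0.6 or 1.0 with eCVD and to the opposite sign without.

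- Overall standardized difference: at most 0.022 (passes).
- Within subgroups: +0.08 to +0.28 with eCVD, −0.05 to −0.18 without.
- False ratio of HRs: 1.04–1.14 (RR 2), 1.07–1.26 (RR 3), 1.12–1.49 (RR 5).
- With no prescribing interaction: 1.00–1.01, although 13–15% of pairs still have members in different subgroups.

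A separate simulation (80,000 patients, three runs per scenario, eCVD 25%, log-odds +0.5 and −0.2) gave an overall difference of 0.002, with +0.15 and −0.065 inside the subgroups. The ratios were 1.11 (RR 3) and 1.20 (RR 5), and 1.07 to 1.30 across milder and stronger inputs.

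**4. The eCVD window.** Sections 9.2.2 and 9.7.1 guarantee 6 months of registration; item 4 looks back 12. Section 9.9.1 speaks of at least 12 months of history, which does not agree with the eligibility rule. With a 6-month proxy of assumed 60% sensitivity in the PS, the share of split pairs rises to 26–31%, against 7–15% when 12-month eCVD is in the PS with the interaction present. On its own, without a prescribing interaction, the mismatch moved the ratio of HRs little in a check of the same kind. The sizes in step 3 come from the interaction.

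**5. Bias against random error.** An eCVD share of 20–40% (assumed) leaves 152 × 0.20 = 30 to 152 × 0.40 = 61 events. Power to exclude 1.5 in that subgroup is 30–48%. The 95% CI factor on the ratio of HRs is exp(1.96 √(4/e + 4/(152 − e))), where e is the number of eCVD events: 2.2 at 20% and 1.9 at 40%.

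**6. After the fix.** With PS and matching done within eCVD groups (RR 3), standardized differences inside the groups were at most 0.008 and the null HRs were 0.998 to 1.004.

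**The case against.** The strongest case against is as follows.

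- **Silence is not a method.** A reader might infer that the protocol cuts the whole-cohort match by eCVD. It does not say so. The visible numbering also skips protocol 9.7.5 and SAP 10.5, and removed text cannot be counted as missing. This stands, so the point is limited to what the visible text describes. Nothing shows that the gaps contain a subgroup step.
- **Split pairs.** A reader might infer that pairs divided between subgroups bias the HRs. They do not: the Cox model in section 9.7.3 is described without pair stratification, and without an interaction the ratio stays at 1.00–1.01 despite split pairs. This stands.
- **The mechanism is assumed.** Section 9.7.2 cites the cardiovascular indication to explain change over calendar time. That by itself supports eCVD as a main-effect predictor, which a PS with CVD covariates handles. No text says that a risk factor predicts treatment in opposite directions. This stands as a limit: the interaction is plausible, not shown.
- **Size.** A false ratio of 1.04 to 1.3 lies well inside a CI factor of 1.9 to 2.2, and the analysis is supportive. True, but a wide interval does not remove bias, and the reader would have no table in which to see it.
- **Match loss.** Forcing eCVD into the main match would add to a loss that section 9.7.2 already anticipates, and would tie the main analysis to a 12-month variable that 6 months of registration does not guarantee. This stands, and the fix avoids it.

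**Conclusion.** The point holds in a limited form. The visible plan gives the eCVD subgroups no match or balance check of their own, and its overall check cannot reveal imbalances that cancel between them. Under assumed inputs (eCVD share 25–30%, a risk factor of about 10% prevalence, RR 2–5, prescribing effects that differ by eCVD), the false ratio of subgroup HRs is about 1.04 to 1.3, and about 1.5 at the extreme. These are illustrations, not estimates for this study.

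Two stronger conclusions are not supported. The documents do not show that the subgroup HRs will be biased; that depends on a prescribing interaction they do not establish. Nor is the main result in doubt on this ground: imbalances that cancel leave the whole cohort balanced, so the dual-therapy HR and the planned size of 34,585.4 per group stand. This is a cheap improvement to a supportive analysis.

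**What to change.** Change item 4 of section 9.7.6 only, and leave the main-analysis match as it is.

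1. Define eCVD over a window that eligibility guarantees is observed, reconciling the 12 months of item 4 with the 6-month look-back.
2. Within each database, re-estimate the PS and re-match separately in patients with and without eCVD, keeping the calendar-quarter rule and the caliper.
3. Tabulate standardized differences within each eCVD group and apply the 10% rule there.
4. Report the ratio of the two HRs with its 95% CI, so that the subgroups are compared directly.

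Cost: a few lines of text, one more matching run and one more balance table. No new data are needed. Some matches may be lost in the subgroup analysis. In the simulation the loss was small: matching within groups gave 12,378 + 19,301 = 31,679, 12,429 + 19,139 = 31,568 and 12,238 + 18,905 = 31,143 pairs, against about 31,500 without it. That is only a rough guide, because the description of the simulation includes no calendar-quarter matching.
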